5.2.2 Data scope according to on-treatment (OT analysis)

Date of permanent discontinuation of the randomized treatment strategy

Date of permanent discontinuation of the randomized treatment strategy is defined as follows:

For subjects randomized to rivaroxaban-based strategy:

- two days after last known ingestion of study rivaroxaban. This date is derived from study drug exposure form, as are the other medication start/stop dates in this section.

For subjects randomized to antiplatelet-based strategy:

- two days after last known ingestion of clopidogrel, ASA, or VKA (after NOAF only), whichever comes last.

Censoring of follow-up for subjects in OT analysis

Censoring of follow-up for patients is the efficacy cut-off date, the date of last known clinical status or date of permanent discontinuation of the randomized treatment strategy + 2 days, whichever comes first.

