6.3.1.1.2. Permanent discontinuation of assigned therapy

Any subject who discontinues prematurely the assigned study medication after he/she has been randomized with no intention to restart is defined as having a permanent discontinuation. Study assessments must be continued according to the visit scheme provided under Section 9.1 and the subject treatment flow diagram.

The reason for a permanent discontinuation must be recorded in the eCRF and in the subject's medical records. Study medication assigned to the discontinued subject must not be assigned to another subject.

The assigned therapy must be subject of a permanent discontinuation for any of the following reasons:

- If any AE occurs which is not acceptable in the opinion of the investigator and/or participating subject
- Continuous treatment is required with an excluded medication for the remaining duration of the study
- Calculated CrCl declines below 30 mL/min on 2 consecutive occasions (control within 24 hours) or subject requires dialysis
- Non-compliance with the study medication regimen in the judgment of the investigator
- Pregnancy (as confirmed by serum or urine pregnancy test)
- Development of hepatic disease associated with coagulopathy leading to a clinically relevant bleeding risk in the judgment of the treating physician

It is noted however, that permanent discontinuation of the assigned therapy is discouraged wherever possible. If a subject early permanently discontinues the assigned therapy, clinical follow-up should be continued until the efficacy cut-off date.

In case of permanent discontinuation of the assigned therapy in a subject randomized to the rivaroxaban-based strategy, ASA 75-100 mg once-daily for the remaining duration of the study is recommended if the treating physician considers it safe and the clinical situation allows doing so.

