10.1. General considerations

A general description of the statistical methods to be used to analyze the efficacy and safety of the study drug is outlined below. A more detailed statistical analysis plan (SAP) will be provided in a separate document. Statistical analysis will be performed using SAS; the version used will be specified in the SAP. The SAP will accommodate protocol amendments or unexpected issues in study execution or data that affect planned analyses, and will provide

more details on the analytic approaches, coding guidelines, censoring of time-to-event variables, and output tables and figures.

If not stated otherwise, all efficacy and the safety analyses will be based on findings as confirmed by the Clinical Event Committee (CEC). Definitions of terms and endpoints are located in Sections [16.1](#) and [16.2](#).

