10.2.2. Data scopes

This section was modified with Amendment 3. For details, see Section [15.2](#).

The following data scopes are defined for efficacy and safety analyses.

Data scope according to intention-to-treat principle (ITT analysis)

The ITT data scope includes all outcome events observed from randomization until the efficacy cut-off date (i.e. the day of the primary completion event). The follow-up period for each subject will be as long and complete as possible between randomization up to the visit scheduled after the anticipated efficacy cut-off date is set.

Data scope according to treatment (OT analysis)

The on-treatment data scope includes all outcome events observed from randomization until two days following permanent discontinuation of the randomized treatment strategy. Subjects are off the rivaroxaban-based treatment strategy when rivaroxaban has been permanently discontinued. Subjects are off the antiplatelet-based treatment strategy when both clopidogrel and ASA have been permanently discontinued within the first 3 months or when ASA alone has been permanently discontinued after 3 months, except in case of NOAF and receiving VKA.

Data scope until NOAF (pre-NOAF analysis)

The pre-NOAF data scope includes all outcome events observed from randomization until the NOAF requiring (a switch to) treatment with high dose rivaroxaban or vitamin K antagonists.

Data scope after NOAF (post-NOAF analysis)

The post-NOAF data scope includes all outcome events observed between the treatment switch precipitated by NOAF until the efficacy cut-off date.

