10.3.5. Analysis of the primary efficacy variable

This section was modified with Amendment 3. For details, see Section 15.2.

The analysis of the primary efficacy variable is performed on the Full Analysis Set (FAS). For superiority analysis the follow-up is censored at the last date of known outcome status or at the efficacy cut-off date, whichever comes first. Non-inferiority analysis is carried out under the OT data scope, i.e. follow-up is censored at two days after permanent discontinuation of the randomized treatment strategy. Censoring is assumed independent of the treatment group assignment.

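### SAP 5.2.2 does not implement the protocol's on-treatment censoring rule: the two-day window is apparently counted twice and the control-arm stop rule differs after 3 months (minor correction)

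*SAP*

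**What the plan says.** **Protocol.** Section 10.2.2 runs the on-treatment scope from randomization "until two days following permanent discontinuation of the randomized treatment strategy". Section 10.3.5 repeats this for the non-inferiority analysis: "follow-up is censored at two days after permanent discontinuation of the randomized treatment strategy". Section 6.3.1.1.2 says that a subject who stops study medication early "with no intention to restart is defined as having a permanent discontinuation", with no days added. For the rivaroxaban arm, 10.2.2 looks at rivaroxaban only. For the control arm, both clopidogrel and ASA must have stopped in the first 3 months. Later a subject is off strategy "when ASA alone has been permanently discontinued after 3 months", except for NOAF subjects on VKA. Section 10.1 leaves further detail on "censoring of time-to-event variables" to the SAP.

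**SAP.** Section 5.2.2 dates permanent discontinuation at "two days after last known ingestion of study rivaroxaban" for the rivaroxaban arm. For the control arm it is "two days after last known ingestion of clopidogrel, ASA, or VKA (after NOAF only), whichever comes last", with no split at 3 months. It then censors at the earliest of the efficacy cut-off, the last known clinical status and the "date of permanent discontinuation of the randomized treatment strategy + 2 days, whichever comes first". Section 6.2.1.1 runs the non-inferiority test in this scope, and section 6.5 uses it for an exploratory bleeding analysis. Superiority is tested under ITT.

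**The concern.** The SAP states that it is based on protocol version 3.0 of 17 August 2016, so a version lag does not explain the difference. A programmer who follows SAP 5.2.2 to the letter censors four days after the last dose. One who follows protocol 10.3.5, taking discontinuation as the last dose, censors after two. In the control arm the two texts can also name different drugs as the one that ends treatment.

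The first discrepancy lengthens follow-up in both arms. The second lengthens it in the control arm only. At stake is which events shortly after stopping, or during late clopidogrel use, count in the non-inferiority test. In an open-label trial that rule should be unambiguous before results are seen.

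**Working it through.** **1. The plan's own figures (background).** HR = ln(1 - 0.264)/ln(1 - 0.33) = 0.7654, as in protocol 10.4. The Schoenfeld formula at two-sided 5% and 80% power gives 4 x (1.960 + 0.842)²/(ln 0.7654)², which rounds up to 440 events. Both reproduce.

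**2. The dates.** Both texts applied literally, with discontinuation under the protocol taken as the last qualifying dose and 3 months as 90 days:

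| Subject (no NOAF) | Protocol | SAP as written | SAP, two days added once |
|---|---|---|---|
| Rivaroxaban, last dose day 200 | 202 | 204 | 202 |
| Control, ASA to day 60, clopidogrel to day 80 | 82 | 84 | 82 |
| Control, clopidogrel to day 90, ASA to day 200 | 202 | 204 | 202 |
| Control, ASA to day 95, clopidogrel to day 105 | 97 | 109 | 107 |
| Control, ASA to day 120, clopidogrel to day 300 | 122 | 304 | 302 |

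Adding two days once removes the difference in the first three rows. The last two rows isolate the control-arm rule. Row four lies within the ±15-day window of the day-90 visit.

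**3. Extra events from two extra days.** Planning hazards are -ln(0.67)/540 = 0.000742 per day (control) and -ln(0.736)/540 = 0.000568 per day (rivaroxaban). The documents give no discontinuation rate, so 10%, 30% and 50% stopping by day 540 are assumed. The simple count is 760 x share x 2 x (0.000742 + 0.000568) = 0.20, 0.60 and 1.0 events over both arms. Allowing for events before stopping and for 360 to 720 days of follow-up, it is 0.17, 0.50 and 0.84.

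**4. Sensitivity of the test.** With V = events/4 as in SAP 6.2.1.1, the largest hazard ratio that passes the margin is 1.20 x exp(-1.96/√110) = 0.9955 at 440 events and 0.9957 at 441. One event added to one arm alone moves ln(HR) by about 0.5/110 = 0.0045.

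**5. Simulation, two-day against four-day rule.** Settings: 760 per arm, uniform accrual over 360 days, cut at 440 ITT events, 4,000 trials per setting, upper limit as in SAP 6.2.1.1, stopping equal in both arms and unrelated to risk.

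| True HR | Verdict differs at 10/30/50% stopping | Non-inferiority rate, 2 vs 4 days |
|---|---|---|
| 0.90 | 0.10 / 0.52 / 0.95% | 84.15 vs 84.15; 80.28 vs 80.10; 73.90 vs 73.75% |
| 1.0 | 0.30 / 0.75 / 1.38% | 47.65 vs 47.80; 42.62 vs 42.68; 37.13 vs 37.05% |

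The upper limit moved by 0.0009 to 0.0048 on average. A further set of 4,000 trials per setting covered the planned HR and the margin:

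- At HR 0.7654 the verdict differed in 0, 0.05 and 0.25% of trials.
- At HR 1.20 the type I error was 2.20/2.68/2.58% (two days) against 2.18/2.58/2.63% (four days), within Monte Carlo error.
- Over four hazard ratios and three stopping rates (48,000 trials), no trial that was positive for superiority had a different non-inferiority verdict.

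**6. Control-arm rule, stress case only.** Assume 30% stopping, with 1% or 5% of controls stopping ASA on days 90 to 360 and staying on clopidogrel to cut-off. At 1% affected, the SAP rule adds 1.0-1.1 events and verdicts differ in 1.08% (HR 0.90) and 1.98% (HR 1.0) of trials. At 5% it adds 5.3-5.7 events and verdicts differ in 2.58% and 3.92%. No document supports either the share or the duration.

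**The case against.** **The two-day conflict is partly inferred.** Protocol 6.3.1.1.2 does not tie permanent discontinuation to the last ingestion, and protocol 10.1 leaves censoring detail to the SAP. The SAP also repeats the protocol's outer formula of discontinuation plus two days. This stands, and it is why the double count is called apparent. Nothing visible in the SAP presents a second window as intended, however, and its literal result is still four days.

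**The control-arm difference concerns off-protocol use.** Protocol 8.1 disallows a P2Y12 inhibitor beyond 90 days in this arm. The two rules agree when both drugs stop within 3 months and for NOAF subjects on VKA. The protocol is itself silent on a subject who stops ASA before 3 months and takes clopidogrel beyond. The SAP reads dates from the study drug exposure form, and whether late clopidogrel would be entered there cannot be seen. So few subjects should be affected, possibly none. An on-treatment rule still has to give one answer for deviations.

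**A correction route exists.** SAP 4.1 sends scope allocation to validity review meetings, and 4.6 requires resulting changes to be documented in an amendment. That offers a way to repair the text but does not repair it.

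**A reader might infer that the superiority claim is at risk,** because non-inferiority must be met first. The figures do not support this. At 440 events superiority needs an estimate below exp(-1.96/√110) = 0.8295, while non-inferiority passes up to 0.9955. A trial close to the non-inferiority boundary is therefore far from superiority.

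**Conclusion.** SAP 5.2.2 as written does not match protocol 10.2.2 and 10.3.5 on two points, and the text should be corrected. The size is minor: under one extra event against 440, a non-inferiority verdict changed in at most about 1.4% of trials at HR 0.90 to 1.0, and a net change in the non-inferiority rate of at most 0.2 points. There is almost no effect at the planned HR and no material effect on type I error or on the superiority conclusion.

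These figures assume 10-50% stopping, equal in both arms and unrelated to risk. The last assumption is the weakest, since protocol 6.3.1.1.2 lists adverse events, renal decline and hepatic disease among the reasons to stop. If the hazard were 5 times higher for 30 days after stopping, at 30% stopping, there would be about 2.3-2.5 extra events and different verdicts in 1.6-2.8% of trials. At 20 times the figures are about 8 events and 3.3-4.7%. The documents give no basis for either multiplier, so these results do not raise the severity.

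Nor do the documents support reading a direction of bias into the longer control follow-up, or treating the 1-5% late-clopidogrel scenario as expected.

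**What to change.** Make two edits to SAP 5.2.2 before analysis, documented as SAP 4.6 provides:

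1. Define the discontinuation date as the date of the last qualifying ingestion, and add two days once, in the censoring sentence.
2. Bring the control-arm analysis rule back to protocol 10.2.2: both drugs within the first 3 months, ASA alone thereafter, with the exception for NOAF subjects on VKA. The SAP should also say how it dates a subject who stops ASA before 3 months and continues clopidogrel beyond, because the protocol does not cover that case.

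Both edits concern analysis scope only; treatment instructions are untouched. No new data and no alpha adjustment are needed. In simulation the first edit changes the non-inferiority rate by at most 0.2 points. In the 5% stress case the second lowers it from 79.28 to 78.70% (HR 0.90) and from 42.98 to 42.10% (HR 1.0), at most 0.9 points.

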5.2.3 Data scope pre-NOAF analysis

Date of NOAF requiring treatment with high dose oral anticoagulation

Date NOAF is defined as the date where treatment with high dose oral anticoagulation for NOAF is started. Information is derived from study drug exposure form for Rivaroxaban or VKA in combination with ECG evidence of NOAF.

Censoring of follow-up in pre-NOAF analysis

Censoring of follow-up for subjects is on the efficacy cut-off date, date of last known visit or NOAF date, whichever comes first.

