10.3.5.3. Exploratory analyses of the primary efficacy variable

In the primary analyses, switches to full dose anticoagulation are treated as integral part of the treatment strategy. Pre-NOAF analyses, with censoring at the time of the switch to anticoagulation therapy, are carried out as exploratory analyses. Post-NOAF analyses, with starting at the time of the treatment switch precipitated by NOAF are carried out as exploratory analyses.

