5.2.4 Data scope post-NOAF analysis

Date of NOAF requiring treatment with high dose oral anticoagulation

Date NOAF is defined as the date where treatment with high dose oral anticoagulation for NOAF is started. Information is derived from study drug exposure form for Rivaroxaban or VKA in combination with ECG evidence of NOAF.

Start of follow-up in post-NOAF analysis

Day 1 in post NOAF analysis is the date of NOAF as defined above.

Censoring of follow-up in post-NOAF analysis

Censoring of follow-up for subjects is on the efficacy cut-off date, or date of last known visit, whichever comes first.

Only subjects that start OAC treatment as described in the protocol section 7.1.1.1 and 7.1.2.1 are included from the post-NOAF analysis.

6. Statistical Methodology

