6.5 Other analysis

Pre-NOAF and post-NOAF analysis are carried out as an exploratory analysis for the primary efficacy variable (DTE). On treatment, pre-NOAF and post-NOAF analysis are carried out as an exploratory analysis for the primary safety (PBE) variable. The analyses are done analogue to the superiority HR analysis as described in [6.2.1.2](#) and are visualized in [flowchart 4](#).

The separate components of the adjudicated primary efficacy and safety endpoint are analyzed exploratory and analogue to the superiority HR analysis as described in [6.2.1.2](#). The separate components of the adjudicated primary efficacy and safety endpoint are:,

- All-cause death
- Any stroke
- Myocardial infarction
- Symptomatic valve thrombosis
- Pulmonary embolism
- Deep vein thrombosis
- Non-CNS systemic embolism
- Life-threatening or disabling bleeds (BARC type 3b, 3c or 5)
- Major bleeds (BARC type 3a).

The following details of NOAF are summarized by treatment:

- Subjects with NOAF reported on ECG but without medication switch
- Subjects with medication switch but without ECG evidence of NOAF
- Subjects with both ECG evidence and medication switch

Medication switch here means: requiring treatment with high dose oral anticoagulation as specified in 3.2.

Mean transaortic valve pressure gradient is measured by echocardiogram (TTE or TEE) at screening and at approximately 360 days after randomization. The difference between 360 days and screening is derived and analyzed exploratory by using a t-test.

The analysis the other variables are visualized in [flowchart 2](#) in appendix I.

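### The pre- and post-NOAF data scopes have no rule for subjects switched to full anticoagulation without ECG evidence of NOAF

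*SAP*

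**What the plan says.** - **Event.** SAP 5.2.3: "Date NOAF is defined as the date where treatment with high dose oral anticoagulation for NOAF is started".
- **Derivation.** The next sentence there adds the second condition: "Information is derived from study drug exposure form for Rivaroxaban or VKA in combination with ECG evidence of NOAF".
- **Pre-NOAF censoring.** SAP 5.2.3: "Censoring of follow-up for subjects is on the efficacy cut-off date, date of last known visit or NOAF date, whichever comes first". There is no separate term for a switch.
- **Post-NOAF entry.** SAP 5.2.4 repeats the definition and adds: "Day 1 in post NOAF analysis is the date of NOAF as defined above".
- **Groups foreseen.** SAP 6.5 tabulates three groups by treatment: ECG evidence without a switch, "Subjects with medication switch but without ECG evidence of NOAF", and both. It explains: "Medication switch here means: requiring treatment with high dose oral anticoagulation as specified in 3.2".
- **Protocol rule.** Protocol 10.3.5.3: "Pre-NOAF analyses, with censoring at the time of the switch to anticoagulation therapy, are carried out as exploratory analyses". No ECG condition appears there. Protocol 10.2.2 ends the same scope at NOAF that requires the switch, and Protocol 16.2 makes an ECG recording necessary for the diagnosis.
- **On-treatment scope.** For the control arm, SAP 5.2.2 sets the discontinuation date at "two days after last known ingestion of clopidogrel, ASA, or VKA (after NOAF only), whichever comes last".

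**The concern.** The primary analyses treat the move to full-dose anticoagulation as part of each strategy. The pre-NOAF analyses of DTE and PBE are the planned ones meant to show the comparison before that move: rivaroxaban 10 mg against antiplatelet therapy. If some switched subjects are never censored, their later time on rivaroxaban 20/15 mg or VKA is counted as time on the original regimens. For PBE this mixes in the exposure the analysis is meant to exclude. The post-NOAF analysis loses the same subjects.

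The group is plausible. The day-180 contact is a telephone call that asks whether NOAF has been diagnosed, with no ECG (Protocol 9.2.2). General practitioners are told that a NOAF finding must reach the site before treatment is modified (Protocol 9.2.1). A diagnosis made elsewhere may leave no tracing at the site, and a later ECG can miss an intermittent arrhythmia.

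**Working it through.** No design figure in the documents depends on this rule, so the main check applies the SAP's rules to its own three groups.

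**Step 1. SAP 5.2.3 and 5.2.4 applied to the SAP 6.5 groups**

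| SAP 6.5 group | NOAF date? | Pre-NOAF scope | Post-NOAF scope |
|---|---|---|---|
| ECG evidence and switch | Yes | Censored at the switch | Enters at the switch |
| ECG evidence, no switch | No (no anticoagulant start) | Stays, still on the original regimen | Not included |
| Switch, no ECG evidence | No (second condition fails) | Stays to cut-off or last visit, on 20/15 mg or VKA | No Day 1 |

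The first two rows behave as intended. The third does not match Protocol 10.3.5.3. It also sits badly within SAP 5.2.4, whose closing sentence admits subjects according to the anticoagulant treatment they start and does not mention an ECG.

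**Step 2. How many subjects (illustration only)**

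Inputs: N = 1520 (Protocol synopsis). p is the share of subjects who switch, assumed 10% to 30%. f is the share of switchers without ECG evidence, assumed 5% to 50%. The documents give neither p nor f for randomized subjects.

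Number affected = N × p × f:
- low: 1520 × 0.10 × 0.05 = 7.6, about 8
- 1520 × 0.10 × 0.10 = 15.2, about 15
- 1520 × 0.30 × 0.10 = 45.6, about 46
- high: 1520 × 0.30 × 0.50 = 228

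**Step 3. Share of pre-NOAF follow-up spent on switched therapy**

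Take 540 days of follow-up (the median in Protocol 10.4), a switch at day t, and ignore earlier events.

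s = p·f·(540 − t) / [(1 − p)·540 + p·t + p·f·(540 − t)]

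- p = 0.10, f = 0.05, t = 270: 1.35 / (486 + 27 + 1.35) = 0.3%
- p = 0.10, f = 0.10, t = 30: 5.1 / (486 + 3 + 5.1) = 1.0%
- p = 0.30, f = 0.10, t = 30: 15.3 / (378 + 9 + 15.3) = 3.8%
- p = 0.30, f = 0.50, t = 30: 76.5 / (378 + 9 + 76.5) = 16.5%

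**Step 4. Effect on a DTE hazard ratio**

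The planning hazard ratio reproduces: ln(1 − 0.264) / ln(1 − 0.33) = 0.7654. Assume 0.7654 before the switch and 1.0 after it, with HR ≈ exp[(1 − s) × ln 0.7654]:
- s = 0.3%: 0.766
- s = 1.0%: 0.768
- s = 3.8%: 0.773
- s = 16.5%: 0.80

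**Step 5. The on-treatment scope**

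SAP 5.2.2 can be read in two ways.
- If NOAF there means the date built in 5.2.3, VKA without an ECG does not count. A control subject then leaves the scope soon after ASA stops. Under Protocol 7.1.2.1 that is day 90 for an early switch, or the switch itself if later. A rivaroxaban subject in the same position stays in, because 20/15 mg is still study rivaroxaban.
- If NOAF there means the clinical diagnosis, VKA counts and both subjects stay in.

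SAP 5.2.2 refers to neither the 5.2.3 date nor an ECG, so the text does not decide between them.

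**The case against.** **Requiring an ECG follows the protocol.** Protocol 10.2.2 ties the scope to NOAF, and 16.2 says NOAF is diagnosed by ECG. This stands in part: a reader might infer that the SAP flatly contradicts the protocol, and it does not. The conflict is with 10.3.5.3, where the censoring event is the change of treatment.

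**The phrase about combination may only name data sources.** That is possible, but SAP 6.5 treats ECG evidence and switch as separable, which favours reading them as two conditions.

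**The ECG may be how the indication is established.** The documents do not say whether the exposure form records why VKA was started. This stands as a constraint on the fix. Ending the scope at any VKA intake would wrongly censor subjects given VKA for another reason, such as a venous thrombosis.

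**Validity Review Meetings can settle unclear cases.** SAP 4.1 and 4.6 allow this, and the NOAF-related unscheduled visit includes a 12-lead ECG. Both limit the problem, but neither supplies a rule for the group.

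**The size may be trivial.** This largely stands. The figure of up to 30% in Protocol 10.4 refers to subjects undergoing TAVR. Randomization comes 1-7 days later, AF with an ongoing anticoagulant indication is excluded (Protocol 6.2), and subjects may decline the switch (Protocol 7.1.2.1). A reader might take 30% of 760, or 228 per arm, as the expected number of switchers; the documents do not support that.

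**Conclusion.** The gap is real and limited. As written, SAP 5.2.3 and 5.2.4 give no NOAF date to a group that SAP 6.5 itself lists. That group is left uncensored in the exploratory pre-NOAF analyses of DTE and PBE and has no starting point in the post-NOAF analysis.

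The number affected is not in the documents and may be small. The 8 to 228 subjects and 0.3% to 16.5% of follow-up rest on assumed switch and ECG shares, and the upper ends are ceilings. With 10% switching and 10% of those lacking ECG evidence, about 15 subjects and 1% of follow-up are involved, and the illustrative hazard ratio hardly moves.

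The ITT superiority test does not use this date. A reader might infer that the on-treatment non-inferiority test, which gates superiority, censors the two arms by different rules. That follows under only one of the two readings of SAP 5.2.2, so it is an ambiguity to remove and not a demonstrated asymmetry.

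**What to change.** 1. **SAP 5.2.3.** End the pre-NOAF scope at the start of high-dose oral anticoagulation recorded on the Study Drug Exposure form as given for NOAF, or for atrial flutter handled as NOAF, whether or not ECG evidence is on file. Keep the NOAF indication so that VKA begun for other reasons does not trigger it. If the form does not hold the indication, name the eCRF source that does.
2. **Sensitivity analysis.** Retain the ECG-confirmed definition in this role.
3. **SAP 5.2.4.** State how subjects with a switch but no ECG evidence are handled, and give them a Day 1 if they are included.
4. **SAP 5.2.2.** State that VKA started for NOAF under Protocol 7.1.2.1 counts as on-strategy with or without an ECG on file, so that both arms follow one rule in the non-inferiority scope.

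The cost is SAP wording and one extra run of an exploratory analysis. SAP 4.3 says the exposure form does not accept missing or incomplete start and stop dates, so no new date collection is needed. The wording should be fixed before the data are analysed.

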11.4. Missing data

Every effort will be undertaken to enhance completeness of data.

In time-to-event analysis subjects who have intentionally terminated follow-up will be censored at the time of the efficacy cut-off date. If loss-to-follow-up occurs, follow-up will be censored at the last date of known clinical outcome status.

Unless otherwise specified in the statistical analysis plan, no statistical techniques will be used to impute missing data for continuous or categorical variables. The number of subjects included in each analysis will be reported so that the reader can assess the potential impact of missing data.

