5.2 Data scopes

5.2.1 Data scopes according to intention-to-treat principle (ITT analysis)

Efficacy cut-off date

When the anticipated efficacy cut-off date is set, the sponsor informs each investigational site and all subjects must return to the clinic within 6 weeks in order to have a final assessment. This assessment will coincide with the EOT visit for the subjects under treatment. The efficacy cut-off date is the date when the study treatments are discontinued. This date will be determined by the Executive Committee (see protocol 5.3.3). From this day onwards subjects will be transitioned from the assigned strategy to an appropriate therapy, as per the clinical site standard of care.

Censoring of follow-up in ITT analysis

Censoring of follow-up for patients is on the efficacy cut-off date, or date of last known clinical status collected from Last Clinical Status form, or date of death (by CEC adjudication) whichever comes first.

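### The pre- and post-NOAF scopes end follow-up at an undefined last visit, so read literally most first-event deaths fall outside the exploratory pre-NOAF DTE analysis

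*SAP*

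**What the plan says.** SAP 5.2 defines four data scopes, each with its own rule for the end of follow-up.

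- **ITT (SAP 5.2.1):** the cut-off, "or date of last known clinical status collected from Last Clinical Status form, or date of death (by CEC adjudication) whichever comes first".
- **On-treatment (SAP 5.2.2):** the cut-off, "the date of last known clinical status or date of permanent discontinuation of the randomized treatment strategy + 2 days, whichever comes first".
- **Pre-NOAF (SAP 5.2.3):** "Censoring of follow-up for subjects is on the efficacy cut-off date, date of last known visit or NOAF date, whichever comes first".
- **Post-NOAF (SAP 5.2.4):** "Censoring of follow-up for subjects is on the efficacy cut-off date, or date of last known visit, whichever comes first".

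The protocol describes the two NOAF scopes without reference to visits. Section 10.2.2 says: "The pre-NOAF data scope includes all outcome events observed from randomization until the NOAF requiring (a switch to) treatment" with full-dose anticoagulation, and "The post-NOAF data scope includes all outcome events observed between the treatment switch precipitated by NOAF until the efficacy cut-off date". For loss to follow-up, Protocol 11.4 says that "follow-up will be censored at the last date of known clinical outcome status". SAP 7 lists no changes to the planned analysis.

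Both NOAF scopes are exploratory, for DTE and for the primary bleeding event (PBE) (SAP 6.5; Protocol 10.3.5.3 and 10.3.7).

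**The concern.** A visit date and a clinical-status date are different things. Visits are scheduled at days 30, 90 and 180 and every 180 days after that (Protocol 9.2.2). Outcome information also arrives between visits and after the last one, through general practitioners, referring cardiologists and death registries (Protocol 5.2). If follow-up stops at the last visit, a well-documented death after that visit lies outside the scope.

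This matters because the primary analyses treat the switch to full-dose anticoagulation as part of the strategy. The NOAF scopes are the analyses planned to separate rivaroxaban 10 mg versus antiplatelet therapy from full-dose rivaroxaban versus VKA. If most deaths drop out, DTE in the pre-NOAF scope becomes a largely non-fatal endpoint. It is then not comparable with the ITT result, and a difference in mortality would hardly show in it.

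**Working it through.** **1. The four rules side by side**

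| Scope | Status or visit date | Date of death listed | Other boundary |
|---|---|---|---|
| ITT | last known clinical status | yes | cut-off |
| On-treatment | last known clinical status | no | cut-off; discontinuation + 2 days |
| Pre-NOAF | last known visit | no | cut-off; NOAF date |
| Post-NOAF | last known visit | no | cut-off |

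The SAP gives no reason for the change in the last two rows and does not define the visit date. The documents leave open whether a telephone contact counts, although Visit 4 (day 180) is one.

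**2. One subject.** A subject without NOAF has Visit 4 on day 180 and dies on day 250, before the cut-off. The earliest listed date is day 180, so the death, 70 days later, is outside the pre-NOAF scope. Under Protocol 10.2.2 it is inside.

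**3. The plan's own figure.** This point does not depend on it, but it fixes the event rates used below (Protocol 10.4: 33.0% versus 26.4% at 540 days).
- HR = ln(1 − 0.264) / ln(1 − 0.330) = 0.7654, as stated.
- Events by Schoenfeld = 4(1.96 + 0.8416)² / (ln 0.7654)² = 440 after rounding up, as stated; power with 440 events is 80.1%.
- With 740 per arm, 360 days of accrual and 720 days in total, expected events are 194 + 243 = 437, against the stated 196 + 244 = 440.

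**4. How many DTE events the literal rule removes.** Let s be the share of first DTE events that are deaths, and g the share of non-fatal first events falling after the last visit. If visits happen only while the subject is alive, and no visit falls on the day of death:

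share lost ≈ s + (1 − s) × g

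Simulation at the design rates, with protocol visit days (day 180 counted as a visit) and follow-up uniform over 360 to 720 days, gave g of about 2% to 4%. The mean gap from last visit to death was about 65 days (median about 54). No first-event death was retained, which follows from the construction. Without NOAF censoring, for a cohort of 2 × 740:

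| Assumed s | Events in full | Events left | Lost |
|---|---|---|---|
| 50% | 437 | 214 | 51% |
| 70% | 438 | 127 | 71% |
| 89% | 437 | 46 | 89% |

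A second simulation assumed a 10% NOAF switch by day 540. It gave losses of 41%, 61% and 90% for s of 40%, 60% and 89%. The control-arm proportion with an event fell from about 31% to 18%, 12% and 3%.

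The documents give no value of s for this trial. The 89% is 24/27, from 1-year death (24%) and death or stroke (27%) in the high-risk cohort described in Protocol 3. It is an upper end, because DTE has further non-fatal components and some of those deaths may have followed a stroke.

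**5. Effect on the hazard ratio.** This depends wholly on assumed effects. With HR 1.2 for death and 0.8 for thromboembolic events, the full-scope HR is about s × 1.2 + (1 − s) × 0.8, which is 0.96, 1.04 and 1.16 for s of 40%, 60% and 89%. The literal rule returned 0.80, 0.80 and 0.82, close to the non-fatal effect that was put in. If the two effects are equal, the HR is about unbiased and only events and precision are lost.

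No simulation was run for the post-NOAF scope or for PBE.

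**The case against.** The best defence is that a censoring date applies only to subjects without an event. The SAP uses the word loosely: the ITT rule lists date of death although death is a primary event. The SAS code takes a ready-made event flag and does not show its derivation. Protocol 10.2.2 includes all outcome events, and SAP 7 declares no departure. On that reading no death is lost.

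For the pre-NOAF scope this does not work. The NOAF date sits in the same earliest-of list and must exclude later events, since a stroke after the switch cannot count as pre-NOAF. A list that cuts off events at the NOAF date also cuts them off at the last visit. The post-NOAF list has no NOAF date in it, so there the literal reading is possible but less certain.

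Several other points stand.
- A reader might infer that every death is lost. It is not. A death on a visit day is kept, and so is one covered by a contact recorded on or after the death. A subject with a non-fatal DTE before the last visit still counts as an event.
- A reader might infer that deaths drop out of the bleeding analyses in the same way. All-cause death is not part of PBE; only fatal bleeds and other bleeds after the last visit are exposed.
- All-cause death is also analysed separately as a component (SAP 6.5), so a mortality imbalance would remain visible in the trial.
- Allocation to the scopes is reviewed at validity review meetings, which may update the SAP (SAP 4.1, 4.6). Flowchart 4 (SAP 8.4) covers these analyses, but its figure was not available for this check.

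**Conclusion.** The wording in SAP 5.2.3 and 5.2.4 differs from the other two scopes and conflicts with Protocol 10.2.2 and 11.4, without a declared change. Read literally, most first-event deaths fall outside the pre-NOAF DTE analysis; the post-NOAF wording allows the same.

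The DTE loss is roughly the share of first events that are deaths. The range of about 41% to 90% rests on assumed shares of 40% to 89%, with 89% an upper end, and on visits occurring only before death.

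Two stronger conclusions are not supported. The documents do not show that the pre-NOAF hazard ratio would be biased in a given direction; that needs different effects on death and thromboembolism, which were assumed here. Nor are the trial's main conclusions at risk: the non-inferiority test uses the on-treatment scope and the superiority test the ITT scope, so both tests, alpha, power and sample size are unaffected.

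**What to change.** In SAP 5.2.3 and 5.2.4, replace the last-visit date with the last date of known clinical or outcome status. Add that any adjudicated event, including death, on or before the applicable boundary counts as an event on its own date. The boundary is the efficacy cut-off and, for the pre-NOAF scope, also the NOAF date. The added statement is needed as well as the new date, because a status date recorded before a death would otherwise leave the same gap.

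The cost is one phrase and one sentence in each of two subsections. No new data are needed: SAP 5.2.1 already relies on the Last Clinical Status form and the adjudicated date of death.
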